10.3 Management of Cardiac Left Ventricular Dysfunction

Neratinib must be discontinued for patients who have a symptomatic decrease in LVEF.

- Congestive heart failure (grade 3):

Patients should be monitored for signs and symptoms of CHF (e.g., dyspnea, tachycardia, cough, neck vein distention, cardiomegaly, hepatomegaly, paroxysmal nocturnal dyspnea, orthopnea, peripheral edema). If the patient develops any of these signs and symptoms, neratinib must be held. The investigator must confirm the diagnosis of CHF with either an echocardiogram or a MUGA scan. Once the diagnosis of CHF is confirmed, neratinib must be permanently discontinued.

- Severe refractory/poorly controlled CHF (grade 4):

Neratinib should be discontinued if the patient develops severe refractory/poorly controlled CHF.

For asymptomatic patients, the decision to continue or stop neratinib is based on two factors, the value of the measured ejection fraction and the change in ejection fraction from baseline, which was performed at the time of registration.

10.4 Neratinib Dose Modifications for Hepatic Impairment

Guidelines for dose adjustment of neratinib in the event of liver toxicity are shown in Table 13. Patients who experience \geq Grade 3 diarrhea requiring IV fluid treatment or any signs or symptoms of hepatotoxicity, such as worsening of fatigue, nausea, vomiting, right upper quadrant pain or tenderness, fever, rash, or eosinophilia, should be evaluated for changes in liver function tests. Fractionated bilirubin and prothrombin time should also be collected during hepatotoxicity evaluation.

Table 13: Dose Modifications for Hepatotoxicity

Severity of Hepatotoxicity*	Action

 Grade 3 ALT or AST ($>5-20 \times$ ULN) OR Grade 3 bilirubin ($>3-10 \times$ ULN) 	
 Hold NERLYNX until recovery to \leqGrade 1 Evaluate alternative causes Resume NERLYNX at the next lower dose level if recovery to \leqGrade 1 occurs within 3 weeks. If Grade 3 ALT or AST, or bilirubin occurs again despite one dose reduction, permanently discontinue NERLYNX

 Grade 4 ALT or AST ($>20 \times$ ULN) OR Grade 4 bilirubin ($>10 \times$ ULN) 	
 Permanently discontinue NERLYNX Evaluate alternative causes

ALT=Alanine Aminotransferase; AST=Aspartate Aminotransferase; ULN=Upper Limit Normal

* Per CTCAE v5.0

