7.3 General Treatment Guidelines

If a toxicity is attributed to one of the study drugs, it may be held and the other drug(s) will still be given as scheduled. If a toxicity is not clearly linked to a single drug, then both neratinib and capmatinib may be held. The treating physician may withhold any of the drugs per their discretion and discussion with the principal investigator as needed to maintain patient safety while a toxicity is evaluated and treated. The drug should be resumed after appropriate toxicity management and dose reduced, if indicated as per Section 10 of the protocol.

Patients must receive at least 80% of the scheduled doses of each study medication to be considered evaluable for DLT. Patients with ER+ breast cancer must receive at least 80% of the scheduled dose of AI to be considered evaluable for DLT. However, any patient who experiences DLT, will be counted as a DLT regardless of how many doses received.

As study therapy is given continuously, missed days of treatment will not be made up. A cycle is defined as 28 days regardless of the number of days of treatment received.

In the event the patient experiences intolerable side effect(s) attributed to the endocrine therapy agent(s), the treating physician may withhold the agent per their discretion and discussion with the principal investigator as needed to maintain patient safety while a toxicity is evaluated and treated. The treating physician may change the AI agent administered and prescribe treatment for symptom control, as clinically indicated.

The following delays are allowed except during the DLT assessment period:

- 1) Up to 4 weeks due to study related AEs
- 2) Up to 8 weeks due to non-study related AEs

Unanticipated Dose Interruptions:

Interruptions due to non-study related issues (logistical, natural disaster, etc) are permitted in the case of logistical reasons not related to study therapy, up to 2 cycles of study.

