7.4 Dose Limiting Toxicity (DLT)

DLT is defined as any of the following possibly, probably, or definitely due to study therapy, assessed during the first 2 cycles [56 days]:

- Any death not clearly due to the underlying disease or extraneous causes
- Non- hematologic toxicity
 - Grade 3 or higher non-hematologic toxicity, Grade 3 diarrhea will be considered a DLT only if it lasts \geq 2 days despite prophylaxis and optimal standard medication and medical management.

- Grade 2 diarrhea lasting \geq 5 days despite prophylaxis and optimal standard medical management
- Pulmonary toxicity
 - Any grade of pneumonitis or ILD confirmed not attributable to infection or another etiology.
- Hy's Law case, defined as a patient meeting all of the following criteria:
 - ALT or AST \geq 3 x Upper Limit of Normal (ULN)
 - Total bilirubin >2 x ULN
 - Little or no evidence of cholestasis (alkaline phosphatase <2 x ULN)
 - No other identified explanation for the injury (such as hepatitis A, B, C, or other viral hepatic injury, alcohol ingestion, congestive heart failure).
- Neutropenic fever, defined as per CTCAE version 5.0:
ANC $<1000/\text{mm}^3$ and a single temperature of >38.3 degrees C (101 degrees F) or a sustained temperature of $>=38$ degrees C (100.4 degrees F) for more than one hour.
- Hematologic toxicity
 - Grade 4 neutropenia or thrombocytopenia >7 days
 - Grade 3 thrombocytopenia with bleeding
 - Grade 4 anemia

The targeted maximum DLT rate is 25%, and we will enroll patients in cohorts of size 3.

Table 4. Capmatinib and Neratinib overlapping toxicities

SOC	Capmatinib toxicity (Ref: CDS)	Neratinib toxicity (Ref: USPI and SmPC)
Congenital, familial and genetic disorders	Embryo-Fetal Toxicity	Embryo-Fetal Toxicity
Gastrointestinal disorders	Diarrhoea	Diarrhoea
	Vomiting	Vomiting
	Nausea	Nausea
	Constipation	Abdominal pain*
	Amylase increased	Stomatitis**
	Lipase increased	Dyspepsia
	Acute pancreatitis	Abdominal distension
		Dry mouth

General disorders and administration site conditions	Fatigue ¹	Fatigue
	Weight decreased	Weight decreased
	Back pain	
	Oedema peripheral ²	
	Non-cardiac chest pain ³	
	Pyrexia ⁴	
Hepatobiliary disorders	Alanine aminotransferase increased	Alanine aminotransferase increased
	Aspartate aminotransferase increased	Aspartate aminotransferase increased
	Blood bilirubin increased	Blood bilirubin increased

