Grade 1 (> ULN - 1.5 x ULN)	Maintain dose level
Grade 2 (> 1.5 - 3.0 x ULN)	Omit dose until resolved to ≤ grade 1 or baseline, then resume treatment at the same dose level.
Grade 3 (> 3.0 - 6.0 x ULN)	Omit dose until resolved to ≤ grade 1 or baseline, then resume treatment at ↓ 1 dose level.
Grade 4 (> 6.0 x ULN)	Permanently discontinue participant from capmatinib treatment
HEPATIC	
Isolated Total Bilirubin elevation*	
Grade 1 (> ULN - 1.5 x ULN)	Maintain dose level

Grade 2 ($> 1.5 - 3.0 \times \text{ULN}$)	Omit dose until resolved to \leq grade 1, then If resolved in ≤ 7 days, maintain dose level. If resolved in > 7 days, $\downarrow 1$ dose level
Grade 3 ($> 3.0 - 10.0 \times \text{ULN}$)	Omit dose until resolved to \leq grade 1, then If resolved in ≤ 7 days, $\downarrow 1$ dose level If resolved in > 7 days, permanently discontinue participant from capmatinib treatment
Grade 4 ($> 10.0 \times \text{ULN}$)	Mandatory: Permanently discontinue participant from capmatinib treatment
Isolated AST or ALT elevation	
Grade 1 ($> \text{ULN} - 3 \times \text{ULN}$)	Maintain dose level
Grade 2 ($> 3.0 - 5.0 \times \text{ULN}$)	Maintain dose level
Grade 3 ($> 5.0 - 20.0 \times \text{ULN}$)	Omit dose until resolved to \leq grade 1 (or \leq grade 2 if grade 2 elevation at baseline) then If resolved in ≤ 7 days, then resume treatment at the same dose level If resolved in > 7 days, resume treatment at $\downarrow 1$ dose level
Grade 4 ($> 20.0 \times \text{ULN}$)	Mandatory: Permanently discontinue participant from capmatinib treatment
Combined elevations of AST or ALT and Total Bilirubin ^{b,c,d}	
For participants with normal baseline ALT and AST and total bilirubin value: AST or ALT $> 3.0 \times \text{ULN}$ combined with total bilirubin $> 2.0 \times \text{ULN}$ without evidence of cholestasis or hemolysis OR For participants with elevated baseline AST or ALT or total bilirubin value: [AST or ALT $> 3 \times \text{baseline}$] OR [AST or ALT $> 8.0 \times \text{ULN}$], whichever is lower, combined with [total bilirubin $> 2 \times \text{baseline}$ AND $> 2.0 \times \text{ULN}$] without evidence of cholestasis or hemolysis	Mandatory: Permanently discontinue participant from capmatinib treatment
METABOLIC	
Amylase and/or lipase elevation	
Grade 1 ($> \text{ULN} - 1.5 \times \text{ULN}$)	Maintain dose level
Grade 2 ($> 1.5 - 2.0 \times \text{ULN}; > 2.0 - 5.0 \times \text{ULN}$ and asymptomatic)	Maintain dose level

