Grade 3	
Omit dose until resolved to \leq grade 1, then:
 
If resolved in \leq 7 days, resume treatment at same dose level
 
If resolved in $>$ 7 days, resume treatment at \downarrow 1 dose level

Peripheral edema	
Grade 1 or 2	Maintain dose level.
Grade 3	Omit dose until resolved to \leq Grade 1, then \downarrow 1 dose level
Grade 4	Permanently discontinue capmatinib
Other adverse events	
Grade 1 or 2	
Maintain dose level, consider to initiate appropriate support medication.
 
For any intolerable grade 2 (e.g. limiting instrumental ADL), consider omitting the dose until resolved to \leq grade 1, then then restart either at same dose or \downarrow 1 dose level.

Grade 3	Omit dose until resolved to \leq grade 1, then \downarrow 1 dose level
Grade 4	Permanently discontinue capmatinib

All dose modifications should be based on the worst preceding toxicity.
 
a Common Toxicity Criteria for Adverse Events (CTCAE version 5.0).
 
b “Combined” defined as: total bilirubin increase to the defined threshold concurrently with ALT/AST increase to the defined threshold
 
c “Cholestasis” defined as: ALP elevation ($>$ 2.0 x ULN and R value (ALT/ALP in x ULN) $<$ 2.0) in participants without bone metastases, or elevation of ALP liver fraction in participants with bone metastases
 
d If combined elevations of AST or ALT and total bilirubin do not meet the defined thresholds, please follow the instructions for isolated elevation of total bilirubin and isolated elevation of AST/ALT, and take a conservative action based on the degree of the elevations (e.g. discontinue treatment at the situation when omit dose is needed for one parameter and discontinue treatment is required for another parameter). After all elevations resolve to the defined thresholds that allow treatment re-initiation, re-start the treatment either at the same dose or at one dose lower if meeting a criterion for dose reduction
	

* Note: If total bilirubin $> 3.0 \times$ ULN is due to the indirect (non-conjugated) component only, and hemolysis as the etiology has been ruled out as per institutional guidelines (e.g., review of peripheral blood smear and haptoglobin determination), then \downarrow 1 dose level and continue treatment at the discretion of the investigator.

** Note: antidiarrheal medication is recommended at the first sign of abdominal cramping, loose stools or overt diarrhea

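### Table 13 has no row for combined ALT/AST and bilirubin elevation, so after a Hy's Law event neratinib either has no rule or, at Grade 3, is held and then resumed on recovery alone

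*Combined protocol and SAP*

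**What the plan says.** Four places in the combined protocol and SAP bear on this event.

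- **Section 7.4 (DLT).** A Hy's "Law case, defined as a patient meeting all of the following criteria" is a DLT of the combination. The criteria are ALT or AST at least 3 x ULN, total bilirubin above 2 x ULN, alkaline phosphatase below 2 x ULN, and no other explanation.
- **Section 10.5.2, Table 15 (capmatinib).** The combined row begins "For participants with normal baseline ALT and AST and total bilirubin value". For those patients, ALT or AST above 3 x ULN with bilirubin above 2 x ULN, without cholestasis or hemolysis, is a mandatory permanent stop of capmatinib.
- **Section 10.4, Table 13 (neratinib).** "Guidelines for dose adjustment of neratinib in the event of liver toxicity are shown in Table 13". It has two rows. Grade 3 is ALT/AST above 5 and up to 20 x ULN, or bilirubin above 3 and up to 10 x ULN. The actions are to hold until Grade 1 or less, evaluate alternative causes, and then "Resume NERLYNX at the next lower dose level if recovery to" Grade 1 or less occurs within 3 weeks. A repeat Grade 3 despite one reduction is a permanent stop. Grade 4 is a permanent stop at first occurrence.
- **Section 7.3 (general rules).** For a toxicity attributed to one drug, "it may be held and the other drug(s) will still be given as scheduled". Where attribution is unclear, "If a toxicity is not clearly linked to a single drug, then both neratinib and capmatinib may be held". After a hold, "The drug should be resumed after appropriate toxicity management and dose reduced, if indicated as per Section 10 of the protocol".

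**The concern.** The protocol treats a combined transaminase and bilirubin rise as serious enough to count as a DLT of the pair and to end capmatinib permanently. It does not say what happens to the other drug. The liver signal is shared: Table 4 lists ALT, AST and bilirubin increases for both agents, and section 8.2.2 advises caution when capmatinib is given with drugs of known hepatotoxic risk. When an injury arises on two such drugs, stopping one does not show that the other was innocent.

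What is at stake is patient safety. Staff who follow the tables as written would find no neratinib instruction at the lower end of the Hy's Law range. In the Grade 3 range they would find a restart instruction tied only to speed of recovery.

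**Working it through.** The plan states no figure to reproduce, so the check sets the thresholds side by side and then looks for any other rule that fills the gap.

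**Step 1: thresholds, normal baseline.** The cases below are illustrative. Each assumes alkaline phosphatase below 2 x ULN, no hemolysis and no other cause.

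| ALT/AST (x ULN) | Bilirubin (x ULN) | 7.4 | Table 15, capmatinib | Table 13, neratinib |
|---|---|---|---|---|
| 4 | 2.5 | DLT | Mandatory permanent stop | No row |
| 6 | 2.5 | DLT | Mandatory permanent stop | Hold, evaluate causes, resume one level lower if Grade 1 or less within 3 weeks |
| 4 | 4 | DLT | Mandatory permanent stop | As above |
| 25 | 2.5 | DLT | Mandatory permanent stop | Permanent stop |

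The zone with no neratinib rule is ALT/AST from 3 to 5 x ULN with bilirubin above 2 and up to 3 x ULN. At exactly 3 x ULN the event is a DLT but just misses Table 15, whose threshold is strictly above 3. The hold-and-resume zone is the same event with ALT/AST above 5 and up to 20 x ULN, or bilirubin above 3 and up to 10 x ULN, and neither at Grade 4.

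**Step 2: abnormal baseline.** Eligibility (6.1, item 10) allows ALT/AST up to 3 x ULN, or 5 x ULN with liver metastasis. Table 15's combined row then starts, for ALT/AST, at the lower of 3 x baseline and 8 x ULN. With baseline b = 2 x ULN, min(3 x 2, 8) = 6 x ULN. ALT 4 x with bilirubin 2.5 x ULN falls below that row. The footnote that begins "If combined elevations of AST or ALT and total bilirubin do not meet the defined thresholds" sends the reader to the isolated rows, and the Grade 2 bilirubin row advises omitting capmatinib. Neratinib again has no row.

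**Step 3: does other text supply a neratinib rule?**

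- Table 10 starts at Grade 3, and its footnote sends hepatotoxicity to the specific tables.
- Table 16, combined elevations: the follow-up presumes that capmatinib has been stopped and does not mention neratinib.
- Section 10.5.3, liver injury work-up: history, laboratory tests, imaging, a PK sample, causality assessment and SAE reporting. No neratinib dose action.
- Section 12.2.3: each SAE must be attributed to each study drug. No dose action follows.
- Section 7.3: holds are permissive. The resume sentence defers to Section 10, which has no row for the lower zone.
- Section 7.6, items 6 and 7: stopping by judgment, with no laboratory trigger.

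None of these requires that neratinib be held or stopped for this event.

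**Step 4: frequency.** In Table 6, on neratinib alone, bilirubin increase of any kind was 4/1408 = 0.28%, ALT increase 120/1408 = 8.5%, and life-threatening ALT increase 3/1408 = 0.2%. A Hy's Law case needs a bilirubin rise and more besides, so 0.28% is a generous guide for that study. It covers early-stage patients on neratinib alone. The documents give no rate for the combination, so I make no projection for the 47 patients here.

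**The case against.** The strongest reply is that the protocol surrounds such a case with review.

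- Table 13 itself requires a hold, an evaluation of alternative causes and recovery to Grade 1 or less before any restart.
- Section 10.5.3 speaks of study treatment generally and wants other causes clarified before drug injury is assumed.
- Section 12.2.3 requires attribution to each drug, and SAEs go to the IND Office and both companies.
- Section 7.6, item 6 lets the IND medical monitor or either company end treatment, not only the investigator.
- Section 7.3 lets the physician withhold any drug while a toxicity is evaluated.
- Single-agent data are reassuring. Table 6 shows no life-threatening bilirubin increase on neratinib, Table 9 lists no hepatic reaction among expected serious reactions in 580 capmatinib patients, and 8.2.2 calls liver test changes on capmatinib alone limited.

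All of this stands, and it makes an unsafe restart unlikely. It does not close the gap. The evaluation in Table 13 has no stated consequence, because resumption turns on recovery time only. The lower zone never reaches Table 13. The remaining provisions permit action without requiring it, whereas for capmatinib the authors chose a mandatory rule.

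A reader might infer that 7.3 orders neratinib to continue after capmatinib is stopped for liver injury. The text does not support that. The sentence concerns holding one drug for a toxicity attributed to it, and does not address permanent discontinuation after an event of unclear cause.

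**Conclusion.** The gap is real and narrow. For a Hy's Law event, neratinib has no rule when ALT/AST is 3 to 5 x ULN with bilirubin above 2 and up to 3 x ULN. When either value is Grade 3, it has a hold followed by a recovery-only restart. Only Grade 4, or a repeat Grade 3, forces a permanent stop. This rests on the tables being read as written and, for the mandatory capmatinib stop, on normal baseline liver tests. It merits consideration as a low-frequency safety gap that is cheap to close.

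Three stronger readings go beyond the documents:

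- **Neratinib is restarted automatically or without causality review.** The hold, the recovery condition, the evaluation line and the drug-specific SAE attribution all stand in the text.
- **The dose-finding result is affected.** The event counts as a DLT whatever happens to neratinib afterwards, so DLT counting and the BOIN rules are untouched.
- **The same defect exists for pneumonitis.** Section 8.1.5 calls the neratinib risk theoretical, Table 4 lists it for capmatinib only, and 10.3 already requires a neratinib hold for dyspnea or cough while heart failure is checked. That case is debatable and is not part of this point.

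**What to change.** Add a row to Table 13 that overrides the Grade 3 row:

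*ALT or AST with total bilirubin meeting the laboratory Hy's Law criteria in 7.4 or the combined row of Table 15: hold neratinib at once, whatever the attribution, and work up per 10.5.3. If another cause is found, follow the isolated rows. If confirmed with no other cause, do not resume neratinib unless the IND medical monitor approves. Grade 4 remains a permanent stop.*

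Add one sentence to 7.3 stating that its provisions for continuing the other drug and for resuming after a hold do not apply to this event.

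A full mirror of Table 15, with a permanent neratinib stop unless another cause is shown, would also close the gap. The version above is milder and keeps access open where the monitor agrees.

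The cost is one table row and one sentence by amendment, with no added patients or procedures. Section 4.1 already has the IND medical monitor approve dose-level changes, so no new body is needed. The downside is that some neratinib doses will be missed during work-ups that prove negative.

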10.5 Capmatinib Dose Reduction and Toxicity Management

10.5.1 Capmatinib Dose Reduction Levels

Table 14: Dose Reduction Steps for Capmatinib PO

Starting dose level 1	Dose level -1	Dose level -2
capmatinib	400 mg b.i.d.	300 mg b.i.d.

Note: dose reduction should be based on the worst toxicity demonstrated at the last dose.

Dose reduction below 200 mg is not allowed

10.5.2 Capmatinib Treatment Interruption and Dose Reduction Guidance

Table 15. Criteria for Dose Reduction/Interruption And Re-initiation of Capmatinib Treatment for Adverse Drug Reactions

To be considered recommended dose modifications, unless otherwise specified as mandatory in this Table 15. Refer to Table 16 for follow-up evaluations as applicable.

Worst toxicity CTCAE Grade ^a during a cycle of therapy	
No toxicity	Maintain dose level
HEMATOLOGICAL	
Neutrophil count decreased (ANC) Neutropenia	
Grade 1 (ANC $<$ LLN - 1500/mm ³ ; $<$ LLN - $1.5 \times 10^9/L$)	Maintain dose level
Grade 2 (ANC $<$ 1500 - 1000/mm ³ ; $<$ 1.5 - $1.0 \times 10^9/L$)	Maintain dose level
Grade 3 (ANC $<$ 1000 - 500/mm ³ ; $<$ 1.0 - $0.5 \times 10^9/L$)	Omit dose until resolved to \leq grade 2, then: If resolved in \leq 7 days, resume treatment at the same dose level If resolved in $>$ 7 days, then \downarrow 1 dose level
Grade 4 (ANC $<$ 500/mm ³ ; $<$ $0.5 \times 10^9/L$)	Omit dose until resolved to \leq grade 2 and then \downarrow 1 dose level

Febrile neutropenia	
(ANC < 1000/mm ³ (< 1.0 x 10 ⁹ /L), fever > 38.3°C)	Omit dose, then: If resolved in ≤ 7 days, resume treatment at ↓ 1 dose level If resolved in > 7 days, permanently discontinue participant from capmatinib treatment
Platelet count decreased (Thrombocytopenia)	
Grade 1 (PLT < LLN - 75,000/mm ³ ; < LLN - 75 x 10 ⁹ /L)	Maintain dose level
Grade 2 (PLT < 75,000 - 50,000/mm ³ ; < 75 - 50 x 10 ⁹ /L)	Maintain dose level
Grade 3 (PLT < 50,000 - 25,000/mm ³ ; < 50 - 25 x 10 ⁹ /L)	Omit dose until resolved to ≤ grade 2, then: If resolved in ≤ 7 days, then maintain dose level If resolved in > 7 days, then ↓ 1 dose level
Grade 4 (PLT < 25,000/mm ³ ; < 25 x 10 ⁹ /L)	Omit dose until resolved to ≤ grade 2, then ↓ 1 dose level
Hemoglobin decreased (Anemia)	
Grade 1 (Hemoglobin [Hgb] < LLN - 10.0 g/dL; < LLN - 6.2 mmol/L; < LLN - 100 g/L)	Maintain dose level
Grade 2 (Hgb < 10.0 - 8.0 g/dL; < 6.2 – 4.9 mmol/L; < 100 - 80 g/L)	Maintain dose level
Grade 3 (Hgb < 8.0 g/dL; < 4.9 mmol/L; < 80 g/L; transfusion indicated)	Omit dose until resolved to ≤ grade 2, then: If resolved in ≤ 7 days, resume treatment at the same dose level If resolved in > 7 days, then ↓ 1 dose level
Grade 4 (Life-threatening consequences; urgent intervention indicated)	Omit dose until resolved to ≤ grade 2 and then ↓ 1 dose level If toxicity recurs, permanently discontinue participant from capmatinib treatment.
RENAL	
Serum creatinine	
Grade 1 (> ULN - 1.5 x ULN)	Maintain dose level
Grade 2 (> 1.5 - 3.0 x ULN)	Omit dose until resolved to ≤ grade 1 or baseline, then resume treatment at the same dose level.
Grade 3 (> 3.0 - 6.0 x ULN)	Omit dose until resolved to ≤ grade 1 or baseline, then resume treatment at ↓ 1 dose level.
Grade 4 (> 6.0 x ULN)	Permanently discontinue participant from capmatinib treatment
HEPATIC	
Isolated Total Bilirubin elevation*	
Grade 1 (> ULN - 1.5 x ULN)	Maintain dose level

Grade 2 ($> 1.5 - 3.0 \times \text{ULN}$)	Omit dose until resolved to \leq grade 1, then If resolved in ≤ 7 days, maintain dose level. If resolved in > 7 days, $\downarrow 1$ dose level
Grade 3 ($> 3.0 - 10.0 \times \text{ULN}$)	Omit dose until resolved to \leq grade 1, then If resolved in ≤ 7 days, $\downarrow 1$ dose level If resolved in > 7 days, permanently discontinue participant from capmatinib treatment
Grade 4 ($> 10.0 \times \text{ULN}$)	Mandatory: Permanently discontinue participant from capmatinib treatment
Isolated AST or ALT elevation	
Grade 1 ($> \text{ULN} - 3 \times \text{ULN}$)	Maintain dose level
Grade 2 ($> 3.0 - 5.0 \times \text{ULN}$)	Maintain dose level
Grade 3 ($> 5.0 - 20.0 \times \text{ULN}$)	Omit dose until resolved to \leq grade 1 (or \leq grade 2 if grade 2 elevation at baseline) then If resolved in ≤ 7 days, then resume treatment at the same dose level If resolved in > 7 days, resume treatment at $\downarrow 1$ dose level
Grade 4 ($> 20.0 \times \text{ULN}$)	Mandatory: Permanently discontinue participant from capmatinib treatment
Combined elevations of AST or ALT and Total Bilirubin ^{b,c,d}	
For participants with normal baseline ALT and AST and total bilirubin value: AST or ALT $> 3.0 \times \text{ULN}$ combined with total bilirubin $> 2.0 \times \text{ULN}$ without evidence of cholestasis or hemolysis OR For participants with elevated baseline AST or ALT or total bilirubin value: [AST or ALT $> 3 \times \text{baseline}$] OR [AST or ALT $> 8.0 \times \text{ULN}$], whichever is lower, combined with [total bilirubin $> 2 \times \text{baseline}$ AND $> 2.0 \times \text{ULN}$] without evidence of cholestasis or hemolysis	Mandatory: Permanently discontinue participant from capmatinib treatment
METABOLIC	
Amylase and/or lipase elevation	
Grade 1 ($> \text{ULN} - 1.5 \times \text{ULN}$)	Maintain dose level
Grade 2 ($> 1.5 - 2.0 \times \text{ULN}; > 2.0 - 5.0 \times \text{ULN}$ and asymptomatic)	Maintain dose level
Grade 3 ($> 2.0 - 5.0 \times \text{ULN}$ with signs or symptoms; $> 5.0 \times \text{ULN}$ and asymptomatic)	Omit the dose until resolved to \leq grade 2, then If resolved in ≤ 14 days, resume treatment at the same dose level

	If resolved in > 14 days, then ↓ 1 dose level
Grade 4 (> 5.0 x ULN with signs or symptoms)	Permanently discontinue participant from capmatinib treatment
CARDIAC	
Electrocardiogram QT corrected (QTc) interval prolonged	
Grade 1 (QTcF 450-480 ms)	Maintain dose level
Grade 2 (QTcF 481-500 ms)	Maintain dose level
Grade 3 (QTcF ≥ 501 ms on at least two separate ECGs)	Omit dose until resolved to ≤ grade 2, then: If resolved in ≤ 7 days, resume treatment at the same dose level If resolved in > 7 days, then ↓ 1 dose level
Grade 4 (QTcF ≥ 501 or > 60 ms change from baseline and Torsades de pointes or polymorphic ventricular tachycardia or signs/symptoms of serious arrhythmia)	Permanently discontinue participant from capmatinib treatment
GASTROINTESTINAL	
Pancreatitis	
Grade 2	Maintain dose level
Grade ≥ 3	Mandatory: Permanently discontinue participant from capmatinib treatment
Diarrhea**	
Grade 1 (despite appropriate anti-diarrheal medication)	Maintain dose level
Grade 2 (despite maximal anti-diarrheal medication)	Omit dose until resolved to ≤ grade 1, then maintain dose level. If diarrhea returns as ≥ grade 2, then omit dose until resolved to ≤ grade 1, then resume treatment at ↓ 1 dose level
Grade 3 or 4 (despite appropriate anti-diarrheal medication)	Omit dose until resolved to ≤ grade 1, then resume treatment at ↓ 1 dose level
Vomiting	
Grade 1 (despite appropriate anti-emetics)	Maintain dose level
Grade 2 (despite appropriate anti-emetics)	Omit dose until resolved to ≤ grade 1, then maintain dose level. If vomiting returns as ≥ grade 2, then omit dose until resolved to ≤ grade 1, then ↓ 1 dose level.
Grade 3 (despite appropriate anti-emetics)	Omit dose until resolved to ≤ grade 1, then ↓ 1 dose level
Grade 4 (despite appropriate anti-emetics)	Omit dose until resolved to ≤ grade 1, then ↓ 1 dose level
Nausea	
Grade 1 or 2 (despite appropriate anti-emetics)	Maintain dose level

Grade 3 (despite appropriate anti-emetics)	Omit dose until resolved to \leq grade 1, then \downarrow 1 dose level
SKIN AND SUBCUTANEOUS TISSUE DISORDERS	
Rash/photosensitivity***	
Grade 1	Maintain dose level
Grade 2	Maintain dose level
Grade 3, despite skin toxicity therapy	Omit dose until resolved to grade \leq 1, then: If resolved in \leq 7 days, then resume treatment at \downarrow 1 dose level If resolved in $>$ 7 days (despite appropriate skin toxicity therapy), then permanently discontinue participant from capmatinib treatment
Grade 4, despite skin toxicity therapy	Omit dose and permanently discontinue participant from capmatinib treatment
RESPIRATORY, THORACIC AND MEDIASTINAL DISORDERS	
ILD /Pneumonitis	
Monitor participants for pulmonary symptoms indicative of ILD/pneumonitis. In addition, withhold capmatinib for acute onset of new or progressive unexplained pulmonary symptoms, such as dyspnea, cough and fever and during diagnostic workup for ILD/pneumonitis to exclude alternative causes such as, but not limited to infections, lymphangitic carcinomatosis, cardiogenic edema, or pulmonary hemorrhage.	
Grade 1	
Interrupt capmatinib during diagnostic workup for ILD/Pneumonitis. Exclude infections and other etiologies.
 
In presence of diagnosis of ILD/Pneumonitis after diagnostic workup, it is mandatory to permanently discontinue capmatinib.
 
Only in the absence of a diagnosis of ILD/Pneumonitis, capmatinib may be restarted at the same dose.
 
If it recurs after resumption of study drug, permanently discontinue capmatinib.

Grade 2	
Mandatory: Interrupt capmatinib dose during diagnostic workup for ILD/pneumonitis until improvement to \leq Grade 1. Exclude infections and other etiologies.
 
In presence of diagnosis of ILD/Pneumonitis after diagnostic workup, it is mandatory to permanently discontinue capmatinib.
 
Only in the absence of a diagnosis of ILD/Pneumonitis, capmatinib may be restarted following these guidelines:
 
 · If resolves to \leq Grade 1 in \leq 7 days reduce study drug by 1 dose level

	
 If fails to resolve to \leq Grade 1 within 7 days or recur after resumption of study drug at decreased dose, permanently discontinue capmatinib
Grade 3 and Grade 4	
Mandatory: Permanently discontinue capmatinib.
 
Treat with IV steroids as clinically indicated. Oxygen therapy as indicated

GENERAL DISORDERS AND ADMINISTRATION SITE CONDITIONS	
Fatigue/ Asthenia	
Grade 1 or 2	Maintain dose level
Grade 3	
Omit dose until resolved to \leq grade 1, then:
 
If resolved in \leq 7 days, resume treatment at same dose level
 
If resolved in $>$ 7 days, resume treatment at \downarrow 1 dose level

Peripheral edema	
Grade 1 or 2	Maintain dose level.
Grade 3	Omit dose until resolved to \leq Grade 1, then \downarrow 1 dose level
Grade 4	Permanently discontinue capmatinib
Other adverse events	
Grade 1 or 2	
Maintain dose level, consider to initiate appropriate support medication.
 
For any intolerable grade 2 (e.g. limiting instrumental ADL), consider omitting the dose until resolved to \leq grade 1, then then restart either at same dose or \downarrow 1 dose level.

Grade 3	Omit dose until resolved to \leq grade 1, then \downarrow 1 dose level
Grade 4	Permanently discontinue capmatinib

All dose modifications should be based on the worst preceding toxicity.
 
a Common Toxicity Criteria for Adverse Events (CTCAE version 5.0).
 
b “Combined” defined as: total bilirubin increase to the defined threshold concurrently with ALT/AST increase to the defined threshold
 
c “Cholestasis” defined as: ALP elevation ($>$ 2.0 x ULN and R value (ALT/ALP in x ULN) $<$ 2.0) in participants without bone metastases, or elevation of ALP liver fraction in participants with bone metastases
 
d If combined elevations of AST or ALT and total bilirubin do not meet the defined thresholds, please follow the instructions for isolated elevation of total bilirubin and isolated elevation of AST/ALT, and take a conservative action based on the degree of the elevations (e.g. discontinue treatment at the situation when omit dose is needed for one parameter and discontinue treatment is required for another parameter). After all elevations resolve to the defined thresholds that allow treatment re-initiation, re-start the treatment either at the same dose or at one dose lower if meeting a criterion for dose reduction
	

* Note: If total bilirubin $> 3.0 \times$ ULN is due to the indirect (non-conjugated) component only, and hemolysis as the etiology has been ruled out as per institutional guidelines (e.g., review of peripheral blood smear and haptoglobin determination), then \downarrow 1 dose level and continue treatment at the discretion of the investigator.

** Note: antidiarrheal medication is recommended at the first sign of abdominal cramping, loose stools or overt diarrhea

*** During the whole duration of treatment with capmatinib, the participant is recommended to use precautionary measures against ultraviolet exposure (e.g., use of sunscreen, protective clothing and avoid sunbathing or using a solarium intensively).

These dose changes must be recorded on the appropriate eCRF.

